9.1.3. Strengths of study design

The strength of the non-interventional study design is that it allows to observe diverse populations in a broad range of settings (natural environment) reflecting reality. All decisions in terms of diagnostic procedures, treatments, management of the disease and resource utilization are fully dependent on mutual agreement between the patient and the attending physician, without interference by a sponsor or study protocol.

9.2. Setting

9.2.1. Eligibility

The study population will consist of patients with metastatic CRC for whom the decision has been taken by the investigator to treat with Stivarga® according to the local summary of product characteristics (SPC).

9.2.2. Inclusion criterion/criteria

- Male or female patients ≥ 18 years of age with metastatic CRC for whom the decision has been taken by the investigator to treat with Stivarga® as 3rd or 4th line treatment
- Patients must have signed an informed consent form

9.2.3. Exclusion criterion/criteria

Not applicable

9.2.4. Withdrawal

Each patient has the right to refuse further participation in the study at any time and without providing any reasons. A patient's participation is to be terminated immediately upon his/her request. The investigator should seek to obtain the reason and record this on the Case Report Form (CRF). In this non-interventional study, withdrawal from the study is independent of the underlying therapy. On the other hand, premature end of therapy does not automatically imply end of documentation: Follow-up continues at least 30 days after end of therapy.

9.2.5. Replacement

Patients will not be replaced after drop-out.

9.2.6. Representativeness

The investigators and the patients documented in the study should be selected only based on eligibility according to inclusion and exclusion criteria as outlined in Section 9.2.2. No further selection should be applied. A representative sample of sites will be included in the study, and investigators will be asked to sample consecutive patients whenever possible to avoid any selection bias and thus to increase likelihood representativeness.

9.2.7. Visits

The start of the study is the date from which information on the first study patient can be first recorded in the study dataset (first patient first visit). A visit is defined as any status assessment or new treatment decision the treating physician takes with the presence of the patient.

The investigator should document at least an initial visit, follow-up visits and a final visit for each patient in the case report form (CRF). Follow-up assessment should be documented every 4 to 6 weeks, although the patient's visit schedule itself will be at the treating physician's discretion. A certain number or frequency of visits is not requested by this protocol, however at least an initial visit and a final visit must be documented.

The observation period for each patient covers the period from start of Stivarga®-therapy to death. The median observation period per patient is estimated to be about 7 months, the study will end 12 months after last patient first visit (also see Section 9.5). The final data collection per patient is at patient's death, at end of study or at any time due to premature discontinuation of observation (whatever is earlier). If the documentation is stopped prematurely, the reasons for the end of observation have to be given. If a patient joins an interventional clinical study during the course of observation, at least the information on survival will still be collected up to the end of this study.

If a patient will still be alive at time of study closure, this will be documented at final observation.

The CRF is available upon request. The respective document is listed in Annex 1.

9.3. Variables

The investigator collects historic data (demographic and clinical characteristics) from medical records if available, or else by interviewing the patient. Likewise, the investigator collects treatment related data during initial visit and follow-up visits.

Table 2: Tabulated overview on variables collected during the study

Schedule Procedure	Base-line	Initial visit	Follow-up	End of therapy	End of observation	Follow-up after end of therapy
Visit date	X	X	X	X	X	X
Patient information and consent	X					
Demographic data	X					
Date of initial CRC diagnosis	X					
Medical history of CRC	X					
Previous treatment for CRC	X					
Concomitant diseases	X					
Weight and height		X				
Tumor status		X				
Performance status (ECOG)		X	X	X	X	
Start of Stivarga® treatment		X				
Initial dose of Stivarga®		X				
Blood pressure		X*				
Laboratory values**		X	X	X	X	
Change of therapy since last visit			X	X	X	
Tumor status evaluation			X	X	X	
Concomitant radiotherapy			X	X	X	
Concurrent diagnostic and therapeutic procedures for mCRC			X	X	X	
Treatment (preventive or therapeutic) for hand foot skin reaction		X	X	X	X	
Concomitant medication		X	X	X	X	
Adverse Events			X	X	X	X***
Date of last Stivarga® dose				X	X	
Reason for discontinuation of treatment				X		
Reason for end of observation					X	
Survival assessment						X
Further treatment for mCRC						X

* weekly up to six weeks from start of therapy

** only documented if new information is available from regular practice. No additional diagnostics are required for the study.

*** for Stivarga®: up to 30 days after end of treatment

9.3.1. Variables to determine the primary endpoint(s)

- Overall survival

9.3.2. Variables to determine the secondary endpoint(s)

- Progression free survival
- Time to progression
- Disease control rate
- Duration of Stivarga® treatment
- Tumor status at different visits
- Incidence of treatment emergent adverse events

9.3.3. Demography

For demographic assessment, the following data will be recorded:

- Year of birth
- Sex
- Ethnicity

9.3.4. Co-morbidities (medical history, concomitant diseases)

9.3.4.1 Colon cancer classification

For the classification of colon cancer the following data will be recorded:

- Histology
- Stage (TNM classification)
- Grading (AJCC)
- Anatomical location
- KRAS mutation
- Date of most recent progression/relapse incl. type of assessment

9.3.4.2 Co-morbidities

Co-morbidities are any medical findings, whether or not they pertain to the study indication, that were present before start of therapy with Stivarga®, independent on whether or not they are still present.

The following co-morbidities are considered to be relevant to the study indication have to be documented:

- Hemorrhagic stroke
- Ischemic stroke
- Transient ischemic attack
- Myocardial infarction

- Angina pectoris
- Congestive cardiac failure including NYHA class
- Hypertension including CTC Grade
- Diabetes mellitus
- Renal insufficiency
- Liver insufficiency
- Leucocytopenia
- Thrombocytopenia
- Hand and foot skin reaction in the past
- Phlebitis in the past 12 months
- Pulmonary embolism in the past 12 months
- Deep vein thrombosis in the past 12 months
- Obesity
- Metabolic syndrome
- Other malignant neoplasm
- Other

9.3.4.3 Diagnosis and prior treatment for CRC

- Prior diagnosis and therapeutic procedures for CRC
- Prior systemic anticancer therapy (medication) with best response for each regimen
- Prior radiotherapy

9.3.5. Prior and concomitant medication

All medication taken in addition to the study drug for any indication (either initiated before study start or during the study) is termed concomitant medication.

9.3.5.1 Concomitant medication except preventive or therapeutic treatment of hand-foot-skin reaction

Information to be collected for concomitant medication includes: trade name or INN, start date, stop date/ongoing, dose, unit, frequency, and indication.

9.3.5.1 Preventive or therapeutic treatment of hand and foot skin reaction

Preventive or therapeutic treatment of hand foot skin reaction with skin cream will be documented on a separate form. Information to be collected includes type of treatment (non-urea based creams, keratolytic creams, topical corticosteroids, topical analgesics, oral analgesics), trade name, total daily dose (only in case of oral analgetics), indication (preventive or therapeutic), start and stop date (or continued)

9.3.6. Concurrent treatment

- Concurrent diagnostic and therapeutic procedures for mCRC

- Concurrent radiotherapy

9.3.7. Laboratory data

It is recommended in the SPC to perform liver function tests (ALT, AST and bilirubin) before initiation of treatment with Stivarga® and monitor closely (at least every 2 weeks) during the first 2 months of treatment. Thereafter, it is recommended to continue periodic monitoring at least monthly and as clinically indicated.

- Total bilirubin
- ALT
- AST

9.3.8. Exposure/treatment

9.3.8.1 At initial visit

Information on Stivarga®-treatment to be documented includes:

- Start date of therapy
- Dose, please specify other dose and reason for other dose
- Treatment time point

9.3.8.2 During follow-up visits

Each dose change and/or interruption of therapy during follow-up must be recorded in a study medication form. The following information must be documented: start/stop date of medication, treatment time point, new daily dose, reason for dose change/interruption.

9.3.9. Vital signs

The following vital signs will be recorded at initial visit:

- Weight (kg)
- Height (cm)
- Blood pressure (once per week up to six weeks from start of therapy)

9.3.10. Visit date(s)

Information on visit date(s) at initial visit and each documented follow-up visit includes:

- Date (day, month, year)

9.3.11. Tumor evaluation

9.3.11.1 At initial visit

The following criteria will be assessed at initial visit:

- Status of tumor
 - Stage
 - Metastasis

- Date of tumor assessment
- Clinical status/radiological status
- ECOG

9.3.11.2 At follow-up visits

The following criteria will be assessed at follow-up visits:

- Tumor status
 - Date of tumor assessment
 - Clinical status/radiological status
- ECOG

9.3.12. Survival status after end of therapy

Typical information to be collected at follow-up after end of therapy includes:

- Request for survival status performed
 - If no: reason for no assessment
 - If yes: survival status
- Documentation of AEs for up to 30 days after last Stivarga[®] intake
- Further anti-cancer therapy (medication) during follow-up
 - Any systemic treatment, if yes, please specify experimental drug or other

9.3.13. Adverse events

New adverse events occurring during the course of study will be documented from the first Stivarga[®] intake until 30 days after end of Stivarga[®] treatment (for further details refer to Section 11.2). Adverse events already documented will be updated with new information during the whole course of the study.

9.3.14. Reasons for choice of treatment

The treating physician will decide on the treatment of the patient based on his medical assessments in close relation to the patient's physical and psychological status. All treatment decisions will follow the real-life treatment behavior of the physician. As there can be expected a wide range of factors influencing treatment decisions over the entire observation period, this will not be captured on the CRF in detail. In any case reasons for stop of Stivarga[®]-treatment will be documented.

9.4. Data sources

The investigator collects historic data (demographic and clinical characteristics) from medical records if available. Likewise, the investigator collects treatment related data, results of tumor assessments and other disease status information, also documented in the medical record, during visits that take place in routine practice. For any adverse events that occur, information is directly obtained from the patient. In case a patient is seen by more than one physician for his/her disease (e.g. the patient is monitored by a physician other than the initial investigator), the initial investigator should make every effort to

collect information on any visits (including results) that have taken place outside the investigator's site due to the patient's disease, for example by interviewing the respective physician or patient or by obtaining an accompanying letter with detailed information and results.

9.5. Study size

Assuming an exponentially distributed OS with a median of 6.4 months, approximately 73% of patients are expected to die within a 12 months observation period. It is aimed to enroll 500 patients in this study. With 500 patients and a loss-to-follow-up of 20% of patients approximately 292 deaths will be observed in a 12-months-time-period. This means that under these assumptions, the 95% confidence interval for the 1-year survival rate of 27% would be approximately (23%, 32%), i.e. of length 9 percentage points. This time frame and number of events seem to be reasonable to describe the Kaplan-Meier-curve for overall survival in the routine daily practice conditions adequately, in particular considering the fact that the pivotal phase III study CORRECT had similar patient numbers randomized to the regorafenib treatment arm (n=505 regorafenib patients valid for ITT analysis).

9.6. Data management

The investigator collects historic data (demographic and clinical characteristics) from medical records if available. Likewise, the investigator collects treatment related data during visits that take place in routine practice.

The CRF is designed in the desktop publishing software, Quick Silver. The CRF will be part of the EDC system which allows documentation of all outcome variables and covariates by all participating sites in a standardized way. A Contract Research Organization (CRO) will be selected and assigned for EDC system development. Information on the EDC system is available upon request. The respective document is listed in Annex 1.

Each patient is identified by a unique central patient identification code. This code is only used for study purposes. The patient code consists of a combination of a country code, site number and patient number. For the duration of the study and afterwards, only the patient's investigator is able to identify the patient based on the patient identification code.

For information on quality control, refer to section 9.8.

9.7. Data analysis

9.7.1. Statistical considerations

Statistical analyses will be of explorative and descriptive nature. The study is not aimed to confirm or reject pre-defined hypotheses.

All variables will be analyzed descriptively with appropriate statistical methods: categorical variables by frequency tables (absolute and relative frequencies) and continuous variables by sample statistics (i.e. mean, standard deviation, minimum, median, quartiles and maximum). Continuous variables will be described by absolute value and as change from baseline per analysis time point, if applicable.

Patients receiving at least one dose of Stivarga® will be included in the analysis. Whenever reasonable, data will be stratified by subgroups (e.g. primary site of disease, baseline ECOG, number of prior treatment lines, KRAS mutation at study entry, concomitant diseases of special interest, location of

metastases, age, sex). In particular, the stratification by the number of prior treatment lines (≤ 4 vs > 4) will be performed in order to account for the changed inclusion criteria.

Sample size and disposition information by analysis time point will be displayed in a frequency table.

All issues concerning patient validity, data consistency checks, permissible data modifications will be described in detail in the Data Management Plan. All statistical issues including derived variables for analysis, handling of missing data and proposed format and content of tables will be detailed in the Statistical Analysis Plan (SAP). The SAP will be finalized before study database lock.

It is planned to have two interim analyses: one analysis of the baseline and safety data approximately 1.5 years after start of study or after half the patients have been enrolled, whatever comes earlier, and a second analysis of efficacy and safety data in July 2016. The final analysis will be performed 12 months after last patient last visit.

9.7.2. Analysis of demography, disease details, prior and concomitant medication and other baseline data

Demographic data, baseline characteristics, diagnosis and prior treatment of CRC, concomitant diseases, and concomitant medication will be described with summary statistics such as mean, SD, minimum, 1, 5, 25, 75, 95, 99 percent quantiles, median, maximum, minimum for continuous variables, and category counts and frequencies (percentages) for categorical variables.. Concomitant medication will be coded using WHO's drug dictionary.

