Amendment-01 is integrated in this protocol. The study protocol was amended due to the medical review of the first 100 recruited patients in this trial. In accordance with current clinical practice guidelines regorafenib should be used as 3rd or 4th line standard option in pretreated patients. Therefore the second inclusion criterion of this study was amended. The recruitment period was extended by 3 months and the number of patients was reduced from 1,000 to 500 due to delays in enrolment.

- Amendment-02, Version 2.0, 2016-04-06, is available as standalone document.

Amendment-02 is integrated in this protocol. The study protocol was amended due to a slower recruitment than planned. The recruitment period was extended by 4 months and the planned date for a second interim analysis was added to the protocol. Additionally, the OS Team composition was updated and minor clarifications regarding the documentation of (S)AEs were made.

6. Milestones

Table 1 presents planned milestones for the project. These milestones are based on a timely review and approval of the project. Administrative changes to milestones due to delays in study preparation and enrolment do not require amendments to the protocol.

Table 1: Milestones

Milestone	Planned date
Start of study	Q4 2013
Start of data collection	Q4 2013
Last patient first visit	31 July 2016
Interim analysis	Q2/2015 or if half the patients are enrolled (whatever is earlier) and a second interim analysis in July 2016
Last patient last visit	Q1 2017
End of data collection (clean database)	Q2 2017
Final report of study results	Q1 2018

7. Rationale and background

Colorectal cancer (CRC) is a disease in which malignant cancer cells form in the tissues of the colon or rectum. The majority of cancer occurring in the colon and rectum are adenocarcinomas, which account for more than 90% of all large bowel tumors. CRC is the fourth most common cancer worldwide, with over one million cases occurring every year. The mortality rate from CRC is approximately half of its global incidence. The five year survival incidence on average is 55%, but is highly variable dependent on the stage of the disease (from 74% for patients with Stage I disease to only 6% for Stage IV patients).

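### The stratification meant to reflect the 3rd/4th-line criterion is cut at 4 prior lines, so 5th-line patients are pooled with those who meet it

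*Protocol*

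**What the plan says.** Section 5 of the protocol reports the reason for Amendment-01: "The study protocol was amended due to the medical review of the first 100 recruited patients in this trial". It then states that "regorafenib should be used as 3rd or 4th line standard option in pretreated patients" and continues: "Therefore the second inclusion criterion of this study was amended". The current criterion in section 9.2.2 requires that "the decision has been taken by the investigator to treat with Stivarga® as 3rd or 4th line treatment".

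Section 9.7.1 analyses every patient who received at least one dose, whichever version of the criterion applied at enrolment. It lists the number of prior treatment lines among several example subgroup factors, without a cut. It then makes one specific commitment: "stratification by the number of prior treatment lines (≤ 4 vs > 4) will be performed", "in order to account for the changed inclusion criteria". No section explains why the boundary is at 4.

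**The concern.** The inclusion criterion counts the line in which Stivarga is given. The stratification counts the lines that came before it. These differ by one, but the number 4 appears as the upper limit in both. That suggests, without proving it, that 4th line became 4 prior lines when the amendment was carried into the analysis section.

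At stake is what the stratified result means. The study is descriptive and tests no hypothesis, so its value lies in estimates that are correctly labelled. A reader will take the ≤4 stratum as the population defined by the amendment and the >4 stratum as the patients outside it. If the strata are programmed as written, the group just outside the criterion sits with those inside it.

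**Working it through.** **Inputs**
- Criterion: Stivarga as 3rd or 4th line (section 9.2.2).
- Strata: ≤4 versus >4 prior lines, intended to account for the changed criterion (section 9.7.1).
- Analysis population: all patients with at least one dose (section 9.7.1).
- Recruited before the change: at least the 100 patients reviewed (section 5). Planned total: 500 (section 9.5).

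**Rule**

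Line in which Stivarga is given = number of prior lines + 1.

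**Classification**

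| Prior lines | Stivarga given as | Meets 9.2.2? | Stratum in 9.7.1 | Stratum with cut ≤3 vs >3 |
|---|---|---|---|---|
| 0 | 1st line | no | ≤4 | ≤3 |
| 1 | 2nd line | no | ≤4 | ≤3 |
| 2 | 3rd line | yes | ≤4 | ≤3 |
| 3 | 4th line | yes | ≤4 | ≤3 |
| 4 | 5th line | **no** | **≤4** | >3 |
| 5 or more | 6th line or later | no | >4 | >3 |

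The row for 4 prior lines carries the point. These patients fail the criterion and are still grouped with those who meet it. The >4 stratum holds only 6th-line or later use. A cut at ≤3 versus >3 puts 5th-line patients on the correct side. Neither cut separates 0 or 1 prior lines from 2 or 3; this matters only if such patients were enrolled.

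**Variant: the cut was meant to refer to the current line.** Then ≤4 versus >4 means 4th line or earlier versus 5th line or later. This is the same split as ≤3 versus >3 prior lines and would serve the purpose. But the text names prior lines, and a programmer following it would build the strata in the fifth column's predecessor, the one headed 9.7.1.

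**Size.** At least 100/500 = 20% of the planned enrolment was recruited before the amendment. That is a floor for recruitment under the earlier rule, not a count of misplaced patients. The protocol gives neither the criterion as it stood before Amendment-01 nor the distribution of prior lines, so the number with exactly 4 prior lines cannot be computed.

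**The case against.** The strongest defence is that the protocol never defines a prior line. Section 9.3.4.3 records prior systemic therapy for CRC by regimen, not only for metastatic disease, and section 8.2 names early relapse after adjuvant treatment as a possible prognostic factor. If an adjuvant regimen counts as a prior line, a patient with adjuvant therapy and 3 metastatic lines has 4 prior lines and is a genuine 4th-line patient, whom the ≤4 stratum places correctly.

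This stands as far as it goes, and it means that a bare switch to 3 prior lines is not enough without a counting rule. It does not rescue the cut. Under the same count, a patient with no adjuvant therapy and 4 metastatic lines also has 4 prior lines, is treated in 5th line, and falls in the same stratum. The protocol does not offer this rationale either.

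A second defence is that derived variables are left to the SAP. That is true in general, but here the protocol itself fixes both the cut and its purpose. An SAP that follows it inherits the mismatch.

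Four stronger readings are tempting, and the document does not support them:
- **That 1st- or 2nd-line patients are in the ≤4 stratum.** The indication covers patients not considered candidates for the listed therapies, so such patients are possible. Nothing shows that any were enrolled.
- **That this is the only way to isolate 3rd/4th-line patients.** Sections 9.7.1, 9.7.5 and 9.7.6 allow other analyses by baseline factors, including number of prior lines. This is, however, the only one committed to for the changed criterion.
- **That a correct cut would separate patients enrolled before and after Amendment-01.** No cut on prior lines can do this, because earlier patients may also have been treated in 3rd or 4th line.
- **That the primary result is compromised.** It is the Kaplan-Meier estimate in all treated patients and does not use the strata.

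**Conclusion.** The point holds in a limited form. As written, the ≤4 stratum combines patients who meet section 9.2.2 with 5th-line patients who do not, so its survival and safety results are not estimates for 3rd/4th-line use. This rests on one assumption: that a line is counted the same way in sections 9.2.2 and 9.7.1, so that 3rd or 4th line means 2 or 3 prior lines.

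The number of patients misplaced is unknown and cannot be estimated from the protocol. The overall survival estimate and the sample size do not change, and with no hypothesis test planned there is no error rate to protect. The effect is confined to the interpretation of one committed descriptive stratification. It should be corrected, but it does not threaten the study.

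**What to change.** In section 9.7.1, or in the SAP with a note that it departs from the protocol text, replace the cut by the line in which Stivarga is given: 4th line or earlier versus 5th line or later, equivalent to ≤3 versus >3 prior lines. State that lines are counted as in the inclusion criterion and whether adjuvant regimens count. If any patients have fewer than 2 prior lines, show them separately, so that the remaining stratum is exactly 3rd/4th-line use. If the boundary at 4 prior lines was intended, give the reason and do not describe the stratum as reflecting the amended criterion.

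The cost is a sentence or two of text and relabelled tables. Prior systemic therapy is already collected by regimen, so no new data are needed, and section 9.7.1 requires the SAP to be final only before database lock.
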